9.0 Study Withdrawal/Discontinuation

Participants may withdraw from the study at any time and continue standard care. Participants may be withdrawn if deemed medically necessary by an attending physician or study staff or if exclusion criteria are met. Participants may be withdrawn from the study by the principal investigator for repeated non-compliance. This would entail altering the seed placement for example. Participants will be reminded that participation will not affect their clinical services and the CSQ8 parental satisfaction survey will be provided to parents of participants.

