3.0 Animal Studies and Previous Human Studies

There is a multitude of research, which has demonstrated efficacy and safety of acupuncture and acupressure in the neonatal and pediatric population; including research within MCJCHV by the PI yielding no adverse outcomes (28). This treatment has also exhibited therapeutic results in veterinary medicine (40). In pediatrics, acupuncture has demonstrated improved myofascial pain and postoperative nausea/vomiting (41, 42). For infants, acupuncture and acupressure has reduced crying in infants with colic and reduced pain during procedures (14, 19, 22, 43). Incidentally, these positive effects can lead to better attachment with mothers. Several studies have outlined the presence of active ear points in the neonate which propose the use of auricular acupuncture or acupressure should be considered as an adjunct treatment (44-47). More specific research studies in NAS reveal acupuncture and acupressure are practical non-pharmacologic interventions (1, 9). Laser acupuncture has been performed on infants with NAS and resulted in reduction in morphine use, diarrhea, length of stay and improved feeding as well as sleep (23-25). Acupressure in combination with massage has also demonstrated efficacy in premature infants weight gain (21). Acupressure is the least invasive technique and very well tolerated (48). A similar study performed acupressure on NAS infants in 1992-1996 with several limitations but there were no adverse reactions or skin disruption noted (1). In this study, ear seeds were left in place for up to 72 hours, following the NADA protocol without any negative effects. Limitations included lack of control for additional acupressure applied by mothers, lack of blinding (sham), and timely application of the seeds (within 24 hours of birth).

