10.0 Statistical Considerations: Analysis Plan

The study sample will be characterized using descriptive statistics including mean/median, standard deviations/interquartile range, proportions and percentages as outlined below. Benchmarks for success are summarized in Table 2.

Data Analysis Aim 1. The primary goal of this aim is to assess feasibility and implementation of this study including recruitment, retention, and execution of and adherence to the acupressure protocol. Feasibility measures will be reported as frequencies and proportions (% of eligible patients enrolled, % of patients prematurely terminating treatment, % of patients completing all study assessments, % of data collection procedures completed, % of missing medical record data). Feasibility will be determined through the following benchmarks: a) recruitment success: recruitment rate of 2 infants per month over the proposed 24-month time frame (80% of 40 (ex 32) enrolled); b) study retention: retention of >80% of participants through all assessment periods, c) adherence to the acupressure administration protocol: advanced practice providers will record at least 90% of all acupressure sessions in the REDCap database and medical record.

Data Analysis Aim 2. Descriptive data will be generated for the outcomes detailed in Table 2: Aim 2 by treatment group. Given the feasibility goal of this study, we will not conduct formal statistical tests of association between the two treatment groups, but we will provide descriptives by groups and measures of variability. These statistics will inform us of data trends. Descriptives will be generated based on the intent to treat principle.

Data Analysis Aim 3. Parental satisfaction with acupressure as an additional non-pharmacologic intervention will be reported as means with standard deviations and percentiles of the CSQ8 scores within each category of the following: excellent, good, fair and poor. Provider and staff acceptability of acupressure as an additional non-pharmacologic treatment will be measured with the Acceptability of Intervention Measure (AIM), Intervention Appropriateness Measure (IAM), and Feasibility of Intervention Measure (FIM). These measures will be reported as frequency distributions and proportions (% of AIM scores, % of IAM scores, and % of FIM scores).

Table 2: Assessment Measures

Outcomes	Measures	Time Point

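### Section 9.0 lets the investigator remove infants from the study for altered seed placement, which can cause loss in the acupressure arm only, against the intent-to-treat plan and unseen by the pooled retention benchmark

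*Combined protocol and SAP*

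**What the plan says.** Section 9.0 (Study Withdrawal/Discontinuation): "Participants may be withdrawn from the study by the principal investigator for repeated non-compliance". The one illustration follows: "This would entail altering the seed placement for example". No number defines repeated. For what happens afterwards, the section mentions only that care is unaffected and that parents receive the CSQ8.

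Section 10.0 (Analysis Plan), Aim 1: the goal is feasibility, "including recruitment, retention, and execution of and adherence to the acupressure protocol". Two benchmarks matter here. One is "study retention: retention of >80% of participants through all assessment periods", not stated by arm. The other, for adherence, is that "advanced practice providers will record at least 90% of all acupressure sessions in the REDCap database and medical record". The percentage "of patients prematurely terminating treatment" is also reported, with no breakdown by arm or reason. The assessment table in the same section adds the percentage of sticker displacement and reapplication, without a denominator.

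Section 10.0, Aim 2: "Descriptives will be generated based on the intent to treat principle". There are no formal between-group tests.

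Section 6.1 handles continuing skin irritation differently: that infant leaves only the intervention part of the study. Section 5.0 keeps enrolled infants in the study until opioid and/or benzodiazepine cessation unless they are transferred or the parents withdraw; it does not mention removal for non-compliance.

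**The concern.** Adherence is one of the things this pilot sets out to measure, and the withdrawal rule acts on it. An infant whose seeds are repeatedly moved can be taken out of the study by the investigator. Under Sections 7.0 and 11.0 the same person monitors progress and collects the data, and no blinding is stated. Control infants have no study seeds to alter, so the stated example has no counterpart in their arm.

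Two results are exposed. The first is the Aim 2 comparison: intent to treat needs outcomes on everyone randomized, and the plan does not secure outcomes after a withdrawal of this kind. The second is any description of how well seeds stayed in place, if it is taken over the infants who remain. How families handle the seeds is something a later trial would need to know. Section 3.0 itself says of the earlier acupressure study: "Limitations included lack of control for additional acupressure applied by mothers". That is not the same behaviour as altering placement, but it shows that the authors regard family handling as relevant.

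**Working it through.** **1. The plan's own figure.** Section 10.0 gives 80% of 40 as 32 for recruitment: 0.80 × 40 = 32, which reproduces. There is no power calculation or planned adherence rate to check.

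**2. Leaving the study versus stopping the intervention.**
- Section 6.1, continuing skin irritation: out of the intervention part only.
- Section 7.0, same event: withdrawn from the study.
- Section 9.0, repeated non-compliance: withdrawn from the study.

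The protocol therefore has the distinction available but applies it unevenly. Sections 5.0, 6.1, 7.0 and 9.0 need to be reconciled.

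**3. What pooled retention can hide.** Inputs: 40 infants, 20 per arm (Sections 2.0 and 4.0); benchmark above 80% (Section 10.0).
- 32/40 = 80.0% is not above 80%, so at least 33 must be retained and 40 − 33 = 7 may be lost.
- All 7 in the acupressure arm: pooled 33/40 = 82.5%, pass; arm 13/20 = 65%.
- 4 in the acupressure arm: pooled 36/40 = 90%, pass; arm 16/20 = 80%, which would not exceed 80%.
- Applied to one arm, the benchmark would need 17/20 = 85%.
- If only the recruitment target of 32 is met (16 per arm assumed): 0.80 × 32 = 25.6, so 26 are needed and 6 may be lost; pooled 26/32 = 81.3%, arm 10/16 = 62.5%.

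**4. Placement-based adherence.** Assumptions not in the documents: 6 sessions per infant, 95% correct placement in compliant infants, 50% in non-compliant infants, withdrawal after session 2.

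| Withdrawn of 20 | All sessions kept | Sessions cut off at withdrawal | Withdrawn infants excluded |
|---|---|---|---|
| 2 | (102.6 + 6)/120 = 90.5% | (102.6 + 2)/112 = 93.4% | 95.0% |
| 4 | (91.2 + 12)/120 = 86.0% | (91.2 + 4)/104 = 91.5% | 95.0% |

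Here 102.6 = 18 × 6 × 0.95 and 91.2 = 16 × 6 × 0.95. Varying this over 4 to 10 sessions, 1 to 4 withdrawals and 0 to 50% placement in non-compliers, the gain over keeping all sessions is about 1 to 14.5 points (cut off) or 2 to 19 points (excluded).

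**5. The stated 90% benchmark.** It is the share of sessions recorded by providers. At an assumed 92% recording rate unrelated to compliance, 0, 2 or 4 withdrawals change the sessions due from 120 to 112 or 104, and the share stays at 92%.

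**The case against.** The best defence is that these failures do not vanish. A withdrawn infant counts against retention and, on an ordinary reading, in the premature-termination percentage. Because the non-compliance must be repeated, the earlier displacements should already be on record. Intent to treat is stated for Aim 2, its outcomes are standard-of-care measures taken from the chart, and no formal test depends on them. Withdrawal is optional, and transfer, worsening illness, death or parental choice can remove infants from either arm.

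Most of this stands and limits the point. It does not remove it: neither retention nor premature termination is broken down by arm or reason, and a stated analysis principle does not supply data that the protocol may have stopped collecting.

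A reader might infer three stronger things:
- **That withdrawals could lift the trial over its 90% adherence mark.** The documents do not support this, because the mark measures documentation; a session with altered seeds counts if it is recorded.
- **That wean, dose and WAT-1 data stop at withdrawal.** The documents do not say so. They only fail to say that collection continues.
- **That Aim 2 would be biased in favour of acupressure.** That needs the removed infants to be the more distressed ones, for which the documents give no evidence.

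**Conclusion.** The point holds as a conflict between a stated rule and the stated analysis. Section 9.0 permits discretionary removal from the study for a reason whose only example is confined to one arm; Section 10.0 promises intent-to-treat descriptives without securing the data for them.

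The size is a bound, not a forecast. With 20 infants per arm, up to 7 losses could all fall in the acupressure arm (65% retained) while pooled retention still passes at 82.5%. The number of infants who would actually be withdrawn for this reason is unknown. The possible gain of about 1 to 19 points in a placement-based rate rests on the assumptions listed and on a denominator that follows only remaining sessions or infants; the plan does not fix that denominator. The direction of any effect on Aim 2 cannot be determined from the documents.

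The change should be made. No hypothesis test is at risk, but the adherence and arm-level summaries are what a later trial would draw on.

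**What to change.** Amend Section 9.0 so that non-compliance with seed placement can lead at most to withdrawal from the intervention, matching the approach in Section 6.1. State that the infant stays in the study in the randomized arm and that all chart-based Aim 2 data are collected to the planned end, unless the parents withdraw from the study. Reconcile Sections 5.0, 6.1 and 7.0 with this. Whether and when acupressure is stopped remains the investigators' decision.

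In Section 10.0:
- record altered placement at each sticker check as an adherence outcome;
- count infants stopped for this reason as non-adherent among all infants randomized to acupressure;
- report retention and premature termination by arm, with reasons.

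The cost is a short amendment and one field on the sticker-check record. No new assessments are needed, since the Aim 2 outcomes are already standard-of-care records. The downside is a less favourable adherence figure and some dilution of the Aim 2 contrast, which intent to treat already accepts.

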10.0 Statistical Considerations: Analysis Plan

The study sample will be characterized using descriptive statistics including mean/median, standard deviations/interquartile range, proportions and percentages as outlined below. Benchmarks for success are summarized in Table 2.

Data Analysis Aim 1. The primary goal of this aim is to assess feasibility and implementation of this study including recruitment, retention, and execution of and adherence to the acupressure protocol. Feasibility measures will be reported as frequencies and proportions (% of eligible patients enrolled, % of patients prematurely terminating treatment, % of patients completing all study assessments, % of data collection procedures completed, % of missing medical record data). Feasibility will be determined through the following benchmarks: a) recruitment success: recruitment rate of 2 infants per month over the proposed 24-month time frame (80% of 40 (ex 32) enrolled); b) study retention: retention of >80% of participants through all assessment periods, c) adherence to the acupressure administration protocol: advanced practice providers will record at least 90% of all acupressure sessions in the REDCap database and medical record.

Data Analysis Aim 2. Descriptive data will be generated for the outcomes detailed in Table 2: Aim 2 by treatment group. Given the feasibility goal of this study, we will not conduct formal statistical tests of association between the two treatment groups, but we will provide descriptives by groups and measures of variability. These statistics will inform us of data trends. Descriptives will be generated based on the intent to treat principle.

Data Analysis Aim 3. Parental satisfaction with acupressure as an additional non-pharmacologic intervention will be reported as means with standard deviations and percentiles of the CSQ8 scores within each category of the following: excellent, good, fair and poor. Provider and staff acceptability of acupressure as an additional non-pharmacologic treatment will be measured with the Acceptability of Intervention Measure (AIM), Intervention Appropriateness Measure (IAM), and Feasibility of Intervention Measure (FIM). These measures will be reported as frequency distributions and proportions (% of AIM scores, % of IAM scores, and % of FIM scores).

Table 2: Assessment Measures

Outcomes	Measures	Time Point
Aim 1 Feasibility of Acupressure Protocol	Demographics: age median & interquartile range, weight median & interquartile range, % male/female, % race (black, white, Hispanic)	Duration of study
	Recruitment Metrics: % of eligible patients enrolled, % of patients prematurely terminating treatment, % of patients completing all study assessments, % of data collection procedures completed, % of missing medical record data	Duration of study
	Enrollment Metrics: % of eligible patients enrolled, % of patients prematurely terminating treatment, % of patients completing all study assessments, % of data collection procedures completed, % of missing medical record data	Duration of study

	Acupressure Administration: % sticker displacement & reapplication, adverse events Infant Activity, Non-Pharmacologic Treatments	Every 24-72 hours Every 6 hours
Aim 2 Acupressure Efficacy	Duration of Medication Exposure (days): median, interquartile range Duration of Wean Phase (days): median, interquartile range Duration of Mechanical Ventilation (days): median, interquartile range Total Medication Equivalents (mg/kg/pt): median, interquartile range Hospital Length of Stay (days): median, interquartile range Exposure to adjunct medications: median, interquartile range WAT-1 Scores: median, interquartile range psCAM-ICU Scores: median, interquartile range RASS Scores: median, interquartile range FLACC Scores: median, interquartile range	Duration of study Duration of study Duration of study Every 24 hours Duration of study Every 24 hours Every 6 hours Every 12 hours Every 2-4 hours Every 4 hours
Aim 3 Acceptability	Parental Satisfaction: CSQ8 means, SD, % scores Staff/Provider Acceptability: % AIM scores, % IAM scores, % FIM scores Qualitative Feedback	Duration of study Completion of Study Every 24-72 hours

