In addition to therapeutic utility of acupressure, it may be cost effective by decreasing hospital stays and the need for more expensive and invasive pharmacologic interventions (9). **In this pilot feasibility study, acupressure will be used as an additional intervention to current, standard therapies.** The Near-Term Infant conceptual framework (NTI) guided the creation of our acupressure protocol to ensure incorporation of standard of care as well as optimization of acupressure elements to produce healthy outcomes in infants at risk for developing iatrogenic withdrawal syndrome. This acupressure protocol has been implemented at MCJCHV in the neonatal abstinence syndrome (NAS) population and was deemed feasible, accepted by healthcare providers and mothers, as well as safe. If proven feasible and beneficial within a PCICU population, further studies may be conducted to evaluate the efficacy of acupressure in easing with withdrawal symptoms as measured by the enhanced withdrawal assessment tool (WAT-1), when applied in conjunction with standard treatments.

Aim 1: Assess feasibility of delivering an acupressure protocol for the treatment of withdrawal in a pediatric cardiac intensive care unit. Feasibility will be assessed with successful completion of the following objectives:

- a. Achieve recruitment and consent of 4 parents per month whose infant has been exposed to opioids and/or benzodiazepines for greater than 5 days, with a retention of 80% or higher during a 24 month time period (n=40).
- b. Deliver the acupressure protocol to 20 infants at risk for developing withdrawal within the standard of care as an additional non-pharmacologic intervention (20 infants will receive standard of care).

Aim 2: Assess impact of auricular acupressure on withdrawal symptoms for an infant physically dependent on opioid and/or benzodiazepine medications. Efficacy of auricular acupressure will be assessed, in line with the standard of care, with comparison of the following assessments among intervention and control groups:

- a. Duration of opioid and/or benzodiazepine exposure
- b. Duration of wean phase
- c. Duration of mechanical ventilation
- d. Total medication dosage as measured in morphine equivalents and benzodiazepine dosages (mg/kg/patient)
- e. Hospital length of stay
- f. Severity of withdrawal symptoms as measured by the Enhanced Withdrawal Assessment Tool (WAT-1)

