4.0 Inclusion/Exclusion Criteria

This prospective pilot study will be conducted over a 24-month period and will enroll a total of 40 infants. Infants will be randomized in a 1:1 ratio to the two groups; randomization will occur within REDCap. Inclusion criteria are as follows: infants, 34 weeks or greater gestation, exposure to opioids and/or benzodiazepine medications for 5 days or more, beginning a stable wean, and maternal age of 18 or older as these individuals are able to consent for themselves (see Table 2). Exclusion criteria will be captured in the medical record as follows: hemodynamic instability, transfer to another facility prior to completion of the weaning regimen or death. Parents identified by health care providers in the PCICU will be approached by study providers ([name], [name], [name], [name], or [name]) in the PCICU. Project procedures will be described and if participants would like to enroll in the study, the consent process will be completed by study providers. Following informed consent, acupressure will be administered within 24 hours MCJCHV. Healthcare providers caring for these infants will be identified through the medical record and subsequent surveys sent through their VUMC email. No ethnic group will be targeted or excluded from this study.

Table 2: Inclusion and Exclusion Criteria

Inclusion	Exclusion
34 weeks gestational age to 1 year of age	Transfer to another facility prior to wean completion
Maternal age 18 or older	Re-escalation of care/Worsening Illness
English speaking	Death
Hemodynamically stable	

Exposure to opioid and/or benzodiazepine for 5 days or more	
---	--

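### The recruitment benchmark for feasibility has three incompatible thresholds, so full planned enrolment over the planned 24 months passes one and fails the other two

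*Combined protocol and SAP*

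**What the plan says.** Section 2.0 introduces the Aim 1 objectives with "Feasibility will be assessed with successful completion of the following objectives". The first, Aim 1a, is "Achieve recruitment and consent of 4 parents per month", "with a retention of 80% or higher during a 24 month time period (n=40"). Aim 1b adds: "Deliver the acupressure protocol to 20 infants at risk for developing withdrawal", with another 20 infants receiving standard care.

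Section 4.0 gives the plan: "This prospective pilot study will be conducted over a 24-month period and will enroll a total of 40 infants", randomised 1:1.

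Section 10.0, Data Analysis Aim 1, says that feasibility is determined by three benchmarks. The recruitment benchmark is "recruitment rate of 2 infants per month over the proposed 24-month time frame (80% of 40 (ex 32) enrolled"). The retention benchmark is "retention of >80% of participants through all assessment periods". The third concerns the recording of acupressure sessions.

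Section 10.0 also states: "Benchmarks for success are summarized in Table 2". The table of that number in Section 10.0 (Assessment Measures) lists metrics and time points, with no recruitment threshold. The other table numbered 2, in Section 4.0, lists eligibility criteria.

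**The concern.** Recruitment has three pass marks in current text: 4 parents per month, 2 infants per month over 24 months, and 32 of 40 infants. The last two stand in one phrase as if they were the same thing. Sections 2.0 and 10.0 each tie their own figure to the feasibility decision, and nothing ranks them.

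No between-group tests are planned, so the feasibility benchmarks are the only success rule fixed in advance, and the protocol makes further efficacy studies depend on feasibility being shown. Actual accrual will be reported whatever happens. Whether it counts as success depends on which sentence is applied, and that choice could be made once accrual is known.

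**Working it through.** **Inputs.** Target 40 infants and period 24 months (Section 4.0); 4 parents per month (Aim 1a); 2 infants per month, and 80% of 40 (Section 10.0).

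**The plan's own figure.** 0.80 × 40 = 32, which reproduces the bracketed count.

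**Does the rate match the count?** 2 × 24 = 48, which is neither 32 nor 40. Conversely, 32 / 24 = 1.33 per month, and 32 infants at 2 per month take 32 / 2 = 16 months.

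**All thresholds on one scale** (one consenting parent per infant assumed):

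| Statement | Total over 24 months | Per month |
|---|---|---|
| Aim 1a | 4 × 24 = 96 | 4 |
| Section 10.0, rate | 2 × 24 = 48 | 2 |
| Section 4.0, plan | 40 | 40 / 24 = 1.67 |
| Section 10.0, count | 32 | 32 / 24 = 1.33 |

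Any total from 32 to 40 spread over the full 24 months passes the count and fails both rates.

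**Readings that might reconcile them.**
- The count as 80% of the rate-based total: 0.80 × 48 = 38.4 and 0.80 × 96 = 76.8. Neither is 32.
- Two consenting parents per infant: 4 parents per month becomes 2 infants per month. Full enrolment gives 2 × 40 / 24 = 3.33 parents per month, still below 4, and 2 infants per month still differs from 1.33 and 1.67.
- Rates judged only until the 40th infant: 2 per month means 40 / 2 = 20 months, and 4 per month means 40 / 4 = 10 months. A fast enough trial then meets all three thresholds; a slower one gets mixed verdicts.

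**How often the verdicts split.** Assume Poisson accrual with mean M per 24 months and the last reading above, which is the lenient one. The count passes if N(24) ≥ 32, with mean M. The 2-per-month rule passes if N(20) ≥ 40, with mean 20M/24. The 4-per-month rule passes if N(10) ≥ 40, with mean 10M/24. Because 40 within 20 months implies at least 32 within 24, and likewise for 40 within 10 months, each split probability is a simple difference.

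| M | 32 in 24 months | 40 in 20 months | 40 in 10 months | Count passes, 2/month fails | Count passes, 4/month fails |
|---|---|---|---|---|---|
| 32 | 0.524 | 0.009 | 3 × 10⁻⁹ | 0.514 | 0.524 |
| 40 | 0.914 | 0.143 | 9 × 10⁻⁷ | 0.771 | 0.914 |
| 48 | 0.994 | 0.521 | 5 × 10⁻⁵ | 0.473 | 0.994 |
| 60 | >0.999 | 0.935 | 0.003 | 0.065 | 0.997 |

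**Secondary checks.** Retention of exactly 80%, such as 32 of 40, meets Aim 1a but not Section 10.0, which needs 33 of 40. Enrolling 32 at 1:1 gives about 32 / 2 = 16 acupressure infants, against the 20 in Aim 1b.

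**The case against.** The best defence is that Section 10.0 is the analysis plan and therefore governs. Its bracket would be the working pass mark, 2 per month would be 1.67 loosely rounded up, and 4 per month would be an aspiration in the aims. This is a natural reading, but the text does not state it. Section 2.0 requires its objectives to be completed successfully, rounding explains neither 32 nor 4, and the clash between 48 and 32 lies inside Section 10.0 itself.

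The probabilities can also be challenged. The 20-month and 10-month rules are derived from an enrolment cap of 40 and are not written in the protocol. Read literally, the rates require 48 and 96 over 24 months, which that cap makes unreachable. This is a fair limit on the model, but the literal reading makes the conflict worse. It is also fair that the 6% at a mean of 60 concerns only the 2-per-month rule; against 4 per month the split is then 99.7%. The contradiction itself needs only the divisions.

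Two further points stand. Recruitment is one of three benchmarks, and no rule says how they combine, so it does not settle feasibility alone. And this is a 40-infant pilot in which no safety rule, data collection or other aim depends on the threshold. What is at stake is the label on the primary aim. The retention and Aim 1b points are minor.

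**Conclusion.** The concern holds. The thresholds equal 96, 48 and 32 over 24 months, against a plan of 40, and full planned enrolment over the planned period gets one pass and two fails. No text settles which applies.

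That result assumes one consenting parent per infant, and two per infant does not remove it. The 77% chance of a split between the count and the 2-per-month rule at the planned accrual rate also assumes Poisson accrual and rates judged up to the 40th infant. Over means of 32 to 60 per 24 months this chance runs from 6% to 77%. The thresholds are not mutually exclusive on that reading, since 40 infants within 10 months would meet all three, but at the planned mean that has a chance of about one in a million.

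This must be fixed, because a stated decision threshold for the primary aim contradicts itself.

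**What to change.** State one recruitment criterion, with unit, count and time window, in the same words in Aim 1a and Section 10.0, and delete the monthly rates that do not match it. Using the plan's own 80% figure, suitable wording is:

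> Recruitment success: at least 32 infants consented and randomised within 24 months (1.33 per month; planned rate 40/24 = 1.67 per month).

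If the sponsor prefers a rate, derive it from a chosen count and window. With 40 infants, 2 per month means completion within 20 months and 4 per month within 10 months, and the 24-month period must then be reconciled with that choice. Put the threshold in the Assessment Measures table, or correct the sentence that points there. Make the change before accrual is interpreted.

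Two smaller edits belong with it:
- State retention once, with one denominator and one inequality, for example at least 80% of all randomised infants (0.80 × 32 = 25.6, so 26 of 32; or 32 of 40).
- Say whether the 20 acupressure infants in Aim 1b are a target or a success condition. If a condition, the recruitment count has to be 40.

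Under the 32-in-24-months wording the cost is protocol text only: sample size, procedures and data collection do not change, though the stated monthly rate becomes less ambitious. Choosing a rate, or a count of 40, would raise the pass mark and may reopen the timeline.

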The study team is comprised of seven specialty trained and credentialed providers that will communicate any issues such as skin irritation to the PI immediately. Adverse events (AE) in this study will be minimal as there are no invasive procedures and the intervention may be administered within the standard of care as the PI has done previously at MCJCHV; with no reported AE (28). However, AE will be monitored throughout the study and any event will be followed to resolution or stabilization. An AE is defined as any unfavorable medical occurrence in a human study participant, whether or not it is considered to be related to participation in the research. Any AE will be reported to the VUMC IRB immediately. An unanticipated problem (UP) is any incident, experience, or outcome that meets all of the following criteria: a) unexpected given the research procedures and characteristics of the study population, b) related or possibly related to participation in the research and c) suggests that the research places participants or others at a greater risk of harm than was previously known or recognized. We will report any such events to the IRB. The PI will provide continuous, close monitoring of participants at VUMC with prompt reporting of AEs to the IRB and will follow VUMC reporting guidelines.

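### Adverse events have no planned by-arm summary: the analysis plan lists them only under acupressure administration

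*Combined protocol and SAP*

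**What the plan says.** Collection is broad. Section 8.0 states: "An AE is defined as any unfavorable medical occurrence in a human study participant, whether or not it is considered to be related to participation". It adds that "AE will be monitored throughout the study and any event will be followed to resolution or stabilization" and that "Any AE will be reported to the VUMC IRB immediately". Control infants are study participants, so these sentences cover both arms.

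Analysis is narrow. In section 10.0, AEs appear once, in the Aim 1 block of Table 2 (Assessment Measures): "Acupressure Administration: % sticker displacement & reapplication, adverse events". The extracted time-point cell beside that block reads "Every 24-72 hours Every 6 hours". The first interval matches the sticker schedule in section 6.1; the second seems to belong to infant activity and non-pharmacologic treatments. The table layout is broken, so this assignment is likely but not certain.

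On by-arm display, the Aim 2 paragraph says "Descriptive data will be generated for the outcomes detailed in Table 2: Aim 2 by treatment group", and the intent-to-treat sentence stands in the same paragraph. The Aim 1 paragraph promises frequencies and proportions; its list of measures does not name AEs, and it mentions no display by group. No safety analysis appears elsewhere.

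**The concern.** The trial randomises infants 1:1 to acupressure or standard care, so a concurrent comparator for safety exists. The analysis plan does not say that it will be used. Section 4 of the background (section 2.0 of the protocol) lists vomiting, diarrhoea, temperature instability and tachypnoea among the symptoms of iatrogenic withdrawal, and any of these could meet the section 8.0 definition without acupressure playing a part. If AEs are reported only alongside sticker displacement, a count in the treated arm stands alone and cannot be read as either reassuring or worrying.

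There is also a question of ascertainment. The acupressure providers have scheduled contacts with treated infants for sticker checks and rotation; control infants have none. Section 8.0 sets no common schedule for looking for AEs in the two arms, so more may be found in the arm that is visited more. Because the results are meant to inform further studies, an AE count without a comparator would carry little forward.

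**Working it through.** The plan states no AE rate and no precision target for AEs, so there is no figure of its own to reproduce. The check has two parts.

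**1. The text side by side**

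- Who is covered: section 8.0, any participant, related or not. Table 2, an item within acupressure administration.
- When: section 8.0, throughout the study. Table 2, apparently every 24-72 hours.
- By arm: section 10.0 says so for Aim 2 outcomes. AEs are listed under Aim 1.

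The data should therefore exist for both arms, but no sentence plans their tabulation by arm.

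**2. What the numbers could show**

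Inputs from the documents: 40 infants at 1:1 (section 4.0), so 40/2 = 20 per arm, which agrees with Aim 1b in section 2.0. Assumed input: the proportion p of infants with at least one AE regardless of acupressure, varied because the documents give none.

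Treated arm alone, no acupressure effect: expected infants with an AE = 20p; chance of at least one = 1 - (1 - p)^20.

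- p = 10%: 2 infants; 1 - 0.9^20 = 88%
- p = 30%: 6 infants; 1 - 0.7^20 = 99.9%
- p = 50%: 10 infants; over 99.9%
- p = 60%: 12 infants; over 99.9%
- p = 70%: 14 infants; over 99.9%

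So even at the low end, some AEs in the treated arm are the likely result when acupressure does nothing.

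Both arms tabulated: 95% half-width for the difference in proportions = 1.96 × sqrt(2p(1 - p)/20).

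- p = 10%: 1.96 × sqrt(0.009) = 19 points
- p = 30%: 1.96 × sqrt(0.021) = 28 points
- p = 50%: 1.96 × sqrt(0.025) = 31 points
- p = 70%: 1.96 × sqrt(0.021) = 28 points

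This is a normal approximation and is rough at 10%, where only 2 events per arm are expected. Power to detect a 20-point excess from a background of 10% to 70% is about 25% to 35% by the normal approximation and 16% to 24% by Fisher's exact test.

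Sticker-site skin irritation, treated arm only: with 0 of 20, the exact two-sided 95% upper limit is 1 - 0.025^(1/20) = 16.8%; the one-sided limit is 1 - 0.05^(1/20) = 13.9%.

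**The case against.** The best defence is that the Table 2 entry means sticker-site effects. It sits beside displacement and reapplication, and section 6.1 speaks of adverse effects such as skin irritation at the same checks. Such effects can occur only in treated infants, so on this reading the row is right as it stands. Section 7.0 names ear-skin irritation as the only known physical risk. It is site-specific and largely attributable without a comparator. This stands, and it is why that item should remain an acupressure-arm measure. It leaves the AEs collected under section 8.0 with no analysis entry at all.

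A reader might infer that AEs are looked for only at sticker checks, or only in the acupressure arm. The documents do not support that: section 8.0 monitors all participants throughout and sends every AE to the IRB, and section 11.0 says data come from the medical record. Unequal detection is a possibility, not something the plan prescribes.

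A reader might also take a high background rate as given. It is not: section 8.0 says "Adverse events (AE) in this study will be minimal as there are no invasive procedures". That expectation sits uneasily with a definition that ignores relatedness, but it means any background figure is an assumption.

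Finally, a by-arm table of 20 against 20 is imprecise, and section 10.0 plans no formal tests. That is true, but the Aim 2 outcomes are shown by arm on the same terms, so small numbers are no reason to leave safety out.

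**Conclusion.** The point holds as a gap in the planned tabulation. Section 8.0 should yield AEs in both arms, but the analysis plan does not commit to summarising them by randomised arm, and its one entry ties them to acupressure administration.

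The size depends on an assumed background: at 10% to 60%, 2 to 12 of 20 treated infants would have an AE with no acupressure effect and no planned control figure beside it.

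It would go too far to conclude that acupressure harms cannot be separated from background events. The known local harm can largely be attributed directly, and a by-arm count of other AEs can be produced from data that section 8.0 already calls for. Nor would that count settle causation: with a 95% half-width of about 19 to 31 points over assumed backgrounds of 10% to 70%, it gives a descriptive comparison and no more. The change is worth making because it costs little. It does not bear on the feasibility benchmarks or the sample size.

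**What to change.** - Add a safety row to Table 2 (Assessment Measures) in section 10.0: infants with at least one AE, number of events, seriousness and relatedness, by randomised arm on the intent-to-treat principle.
- State that AEs are taken from the medical record on the same review schedule in both arms, over the full section 8.0 monitoring period. Infants withdrawn under section 9.0 should stay in the denominator of the arm to which they were randomised.
- Keep sticker-site skin findings as a separate acupressure-arm item, reported with an exact 95% confidence interval.
- Add a sentence that the between-arm AE comparison is descriptive at 20 per arm, and give the expected precision.

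The cost is one table row, two or three sentences, and the same chart review for controls as for treated infants. Section 11.0 already has study data drawn from the medical record, and no additional infants are needed.
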